Trametinib is an orally bioavailable, reversible, highly selective allosteric inhibitor of MEK1/2 which is downstream of Ras/MAPK signaling. Trametinib is FDA-approved for the treatment of adults with advanced melanoma with a BRAF V600E or V600K mutation. It is currently being investigated in over 50 trials as a single agent or in combination with other targeted/cytotoxic therapies in patients with a variety of solid tumors and hematologic malignancies. This trial will evaluate the activity of trametinib in children and adolescents with relapsed or refractory JMML. The planned starting dose is 0.032 mg/kg/day for children aged 1 month to < six years of age and 0.025 mg/kg/day for children six years of age and older. These are the recommended phase 2 doses (RP2D) that were established in a pediatric trial for children with solid tumors. No further dose escalation is planned.

Based on the genetics and predicted biochemical sequelae of increased signaling through the Ras/MAPK pathway, MEK inhibition is a logical treatment approach for patients with JMML. We will collect sequential samples from all patients enrolled to assess the clinical and molecular response at study entry and at disease progression if applicable. This trial will provide an opportunity to interrogate the genetic, biochemical, and functional perturbations of response and resistance to trametinib in patients with JMML.

The primary objective of this study is to determine the response rate to trametinib after twelve cycles of therapy in children with relapsed/refractory JMML. Secondary objectives are (1) to further define and describe the toxicities of trametinib administered as monotherapy (2) to further characterize the pharmacokinetics (steady state trough concentration) of trametinib in children with JMML (3) to prospectively evaluate mutant allele burden as a marker of disease activity in JMML (4) to measure the rate of complete responses in children with JMML and (5) to measure the duration of response among responders.

EXPERIMENTAL DESIGN SCHEMA

Treatment Schema:

*Trametinib is administered orally.

A cycle of therapy is 28 days. Therapy may consist of up to 12 cycles, for a total duration of therapy approximating 12 months, absent disease progression or unacceptable toxicity.

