7.1 End of Therapy & Follow-up

STUDIES TO BE OBTAINED	End of Therapy	Progressive Disease
History	X	
Physical exam with VS	X	
Ht, Wt, BSA	X	

Performance status	X	
Pregnancy test	X	
CBC, differential, platelets	X	
Electrolytes including Ca ⁺⁺ , PO ₄ , Mg ⁺⁺	X	
Creatinine, SGPT (ALT), bilirubin	X	
Total protein/albumin	X	
Bone marrow evaluation	X	
JMML panel using mutation allele burden	X	X
Genomic, Epigenomic and Functional assays*	X	X

*if the patient consented

See COG Late Effects Guidelines for recommended post treatment follow-up:

<http://www.survivorshipguidelines.org/>

Note: Follow-up data are expected to be submitted per the Case Report Forms (CRFs) schedule.

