8.0 CRITERIA FOR REMOVAL FROM PROTOCOL THERAPY AND OFF STUDY CRITERIA

8.1 Criteria for Removal From Protocol Therapy

- a) Progressive disease.
- b) Adverse Events requiring removal from protocol therapy, as stated in [Section 5.0](#).
- c) Patients who receive concurrent anticancer or investigational therapy, as stated in [Section 4.1.4](#).
- d) Refusal of further protocol therapy by patient/parent/guardian.
- e) Completion of 12 cycles of therapy.
- f) Physician determines it is in patient's best interest.
- g) Non-compliance that in the opinion of the investigator does not allow for ongoing participation.
- h) Patients who develop a second malignant neoplasm.

Patients who are removed from protocol therapy (except for 8.1.g) are to be followed until they meet the criteria for Off Study (see below). Follow-up data will be required unless consent was withdrawn.

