8.2 Off Study Criteria

- a) Death.
- b) Lost to follow-up.
- c) Entry into another COG study with tumor therapeutic intent (e.g., at recurrence).
- d) Withdrawal of consent for any further data submission.
- e) The fifth anniversary of the date the patient was enrolled on this study.
- f) Patient did not receive protocol treatment after study enrollment

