9.3 Methods of Analysis

Response criteria are described in [Appendix III](#). A responder is defined as a patient who achieves a best response (as defined in [Section 10.2](#)) of PR or CR on the study prior to having an overall response of PD (as defined in [Section 10.2](#)); all others will be considered non-responders. The evaluation period for determination of the best response will be 12 treatment cycles. Response rates will be calculated as the percent of evaluable patients who are responders, and confidence intervals will be constructed accounting for the two-stage design.

Duration of response (Aim 1.2.5) will be defined as the time from first occurrence of PR or CR until the first occurrence of PD, death, or going off study. Patients who progress will be considered to have had an event, patients who die prior to progressing will be considered to have a competing event, and patients who go off study prior to progressing will be censored at time of last contact. The analysis will be done using the method of Gray.⁴⁵

Toxicity tables will be constructed to summarize the observed incidence by type of toxicity and grade. A patient will be counted only once for a given toxicity for the worst grade of that toxicity reported for that patient. Toxicity information recorded will include the type, severity, time of onset, time of resolution, and the probable association with the study regimen.

The analytic unit for monitoring for protocol-specific toxicities will be the patient-course: Each course where the patient receives the agent and either 1) has a protocol-specific toxicity event, or 2) receives at least 85% of their assigned dose during the cycle will be considered in the analysis. If there is strong evidence (posterior probability of at least 70% with at least 2 observed toxicities) that there is a per course protocol-specific toxicity probability of more than 20%, such information will be presented to the DSMC.

We will use a Bayesian rule to monitor for protocol-specific toxicities. We will assume a beta prior distribution with $\alpha = 0.52$ and $\beta = 2.08$. At least once per month, we will calculate the posterior probability (given the data) that the probability of protocol-specific toxicity exceeds the 20% threshold:

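### Duration of response is censored at last contact, but the protocol times no disease assessment after End of Therapy, so missed or late-found progression counts as continued response

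*Combined protocol and SAP*

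**What the plan says.** Section 9.3 defines duration of response as the "time from first occurrence of PR or CR until the first occurrence of PD, death, or going off study". Progression is the event. For deaths, "patients who die prior to progressing will be considered to have a competing event". For the rest, "patients who go off study prior to progressing will be censored at time of last contact". The analysis is by the method of Gray.

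Section 8.1 sets follow-up after treatment: "Patients who are removed from protocol therapy (except for 8.1.g) are to be followed until they meet the criteria for Off Study". The latest off-study criterion in 8.2 is "The fifth anniversary of the date the patient was enrolled on this study"; death, loss to follow-up, another COG therapeutic study or withdrawal of consent can end it sooner.

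The table in 7.1 has two columns, End of Therapy and Progressive Disease. Physical examination, blood count and marrow are marked only in the first. For the period after therapy, 7.1 points to late-effects guidelines and adds that "Follow-up data are expected to be submitted per the Case Report Forms (CRFs) schedule". In 7.3.1 the mutant allele samples outside the treatment cycles are at baseline, at End of Treatment and at progression.

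**The concern.** Contact is not assessment. Under Appendix III, progression is a measured change in white count, circulating precursors and blasts, platelets, marrow blasts, spleen size, extramedullary disease, karyotype, mutation status or chimerism. Under 10.2, genetic progression alone makes the overall response PD, whatever the clinical status. A responder who finishes Cycle 12, feels well and is reached two years later is in response up to that date under 9.3, even if nothing that could show progression was measured in between.

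The error runs one way. Undetected progression lengthens the recorded response, and progression found late is dated late. What is at stake is the duration curve for a small group of responders. That curve will be read as evidence of durability after treatment stops.

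**Working it through.** **Plan's own figures.** The plan states no numerical target for duration of response, so there is none to reproduce. The Simon design in 9.2 recomputes correctly (type I error 0.0686, printed 0.069; power 0.882) and is not involved here.

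**1. Time without a scheduled assessment.** Inputs: 12 cycles of 28 days; at most 14 days between cycles (4.2.3, 4.3.3, 4.4.3); five years from enrollment (8.2), which is 5 × 365.25 = 1826.25 days; 30.4375 days per month.
- No delays: 12 × 28 = 336 days = 11.0 months. Remaining: (1826.25 − 336) / 30.4375 = 49.0 months, 82% of the window.
- Every gap at its maximum: 336 + 11 × 14 = 490 days = 16.1 months. Remaining: 43.9 months, 73%.

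These are ceilings for a patient who completes 12 cycles and stays on study without PD for five years.

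**2. Possible bias under the present rule.** Assumptions, none from the documents: response at month 3, exponential time to progression with median m, no deaths, contact kept to month 60, and a share q of post-therapy progressions detected at onset with the rest never detected. Let S(t) = 2^(−t/m). End of Therapy falls a = 11.04 − 3 = 8.04 months after response. The estimated share still in response at 24 months is

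S(a) − q × [S(a) − S(24)].

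For m = 12: S(a) = 0.629 and S(24) = 0.250. With q = 0.75 this gives 0.629 − 0.75 × 0.379 = 0.345.

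| True median (months) | True share at 24 months | q = 75% | q = 50% | q = 25% | q = 0 |
|---|---|---|---|---|---|
| 6 | 6% | 15% | 23% | 31% | 40% |
| 12 | 25% | 35% | 44% | 53% | 63% |
| 24 | 50% | 57% | 65% | 72% | 79% |

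With q = 100% the estimate equals the truth.

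**3. Censoring at last assessment, with no new visits.** Patients without recorded PD are then censored at End of Therapy, and only those whose PD is found later stay at risk. With b = 60 − 3 = 57 months, the estimate is

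S(a) × [S(24) − S(b)] / [S(a) − S(b)],

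and q cancels as long as some progressions are found.
- m = 24: 0.793 × (0.500 − 0.193) / (0.793 − 0.193) = 0.41, against a true 0.50.
- m = 12: 0.629 × (0.250 − 0.037) / (0.629 − 0.037) = 0.23, against a true 0.25.

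This rule alone replaces an upward bias with a downward one.

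**4. Both changes together.** Suppose assessments are recorded every three months (an illustrative interval) and each progression is found at the next one. Averaged over where month 24 falls between visits, the estimate is S(24) × [2^(3/m) − 1] / [(3/m) × ln 2].
- m = 12: 0.25 × 0.189 / 0.173 = 0.27, against 0.25.
- m = 24: 0.50 × 0.0905 / 0.0866 = 0.52, against 0.50.

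**5. Small numbers.** Three responders of 20 is the threshold for calling the agent effective; 25% of 20 is 5, and 35%, the top of the table in 9.2, is 7. Moving one censoring date changes the curve only if another responder progresses between the two dates. The step then falls to 1 − 1/n with that patient at risk, or 1 − 1/(n − 1) without:
- n = 3: 0.67 against 0.50
- n = 5: 0.80 against 0.75
- n = 7: 0.86 against 0.83

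**The case against.** The strongest reply is that routine care will find most progressions. Once found, progression is an event under 9.3 and triggers the samples in 7.1 and 7.3.1, and death without progression is handled as a competing event. This stands. A reader might infer that all time after End of Therapy is counted as response regardless, or that the estimate must be biased. The documents do not support that: the bias comes only from progression that is missed or found late.

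Second, the case report forms may ask for disease status with a date. Section 12.0 says that the forms and their submission schedule are posted elsewhere, and they are not in the documents. So it cannot be said that no such data are collected, only that the protocol text sets no assessment.

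Third, a reader might take the exception for 8.1.g to mean that responders removed for non-compliance are not followed at all. The next sentence of 8.1 requires follow-up data unless consent was withdrawn, and non-compliance is not an off-study criterion in 8.2. The sentences conflict, but they do not show that such patients are dropped. Nothing in the documents shows that their risk of progression differs.

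Finally, only a secondary aim is touched and no decision rule uses it. That limits the weight of the point without removing it.

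**Conclusion.** The point holds in this form: censoring at last contact, with no disease assessment timed after End of Therapy in the protocol, lets missed or late-found progression count as continued response and biases duration upward. The exposed period is at most about 44 to 49 months. It is shorter for patients who leave the study early and can be longer for a responder who stops treatment early but stays on study.

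The size of the bias is unknown. The percentages above rest on assumed progression and detection rates and show a possible range, not a forecast. They run from no bias with full detection to 63% against a true 25% with none (12-month median). The effect of one patient's censoring date is large only with about three responders.

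The primary response rate, judged over 12 cycles, and the two-stage design are unaffected.

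**What to change.** Make the first two changes as a pair.

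1. In 9.3, censor patients without PD at the date of the last adequate disease assessment instead of last contact, and define adequate. State whether PD after therapy is clinical only or includes genetic progression; blood counts and spleen size cannot show genetic or marrow progression.
2. In 7.1, add a follow-up column for patients without PD. It should record, with dates, the disease data available from routine visits: blood count with differential, spleen size, and any marrow, karyotype or mutant allele result.

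Change 1 should not be made without change 2, for the reason shown in step 3 of the working. If routine visits prove to be prompted mainly by symptoms, some bias will remain and should be reported.

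Separately, reconcile the two sentences in 8.1 on follow-up after removal under 8.1.g with each other and with 8.2.

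The cost is one revised censoring rule, one table column and a few more dated items in at most 24 patients. That routine visits supply these data is an assumption. Some durations will be shorter than under last-contact censoring.

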9.4 Evaluability for Response

Any patient who is enrolled and receives at least one dose of trametinib will be considered evaluable for response.

9.5 Evaluability for Toxicity

All patients who either (1) receive one dose of trametinib and have a toxicity, or (2) receive at least 85% of the total dose of trametinib according to protocol guidelines during the first cycle of therapy will be considered in the evaluation of toxicity.

9.6 Gender and Minority Accrual Estimates

The gender and minority distribution of the study population is expected to be:

DOMESTIC PLANNED ENROLLMENT REPORT					
Racial Categories	Ethnic Categories				Total
	Not Hispanic or Latino		Hispanic or Latino		
	Female	Male	Female	Male	
American Indian/ Alaska Native	0	0	0	0	0
Asian	1	1	0	0	2
Native Hawaiian or Other Pacific Islander	0	1	0	0	1
Black or African American	1	1	0	0	2
White	4	11	2	2	19
More Than One Race	0	0	0	0	0
Total	6	14	2	2	24

This distribution was derived from AAML0122.

9.7 Analysis of the Pharmacokinetic Parameters

A descriptive analysis of pharmacokinetic (PK) parameters of trametinib will be performed to define systemic exposure, drug clearance, and other pharmacokinetic parameters. The PK parameters will be summarized with simple summary statistics, including means, medians, ranges, and standard deviations (if numbers and distribution permit).

9.8 Analysis of Biological and Correlative Endpoints

Mutant allele burden (as percentages) and trametinib concentrations as measured by mass spectrometry will be analyzed descriptively. Values will be summarized with means, standard deviations, and 95% confidence intervals.

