1.2 Secondary Aims

- 1.2.1 To further define and describe the toxicities of single agent trametinib in children with recurrent or refractory JMML.
- 1.2.2 To further characterize the pharmacokinetics of trametinib in children with recurrent or refractory JMML.
- 1.2.3 To prospectively evaluate mutant allele burden as a marker of disease activity in JMML.
- 1.2.4 To measure the rate of complete responses in children with recurrent or refractory JMML.
- 1.2.5 To measure the duration of response among responders.

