7.2.5 Cytologic Slides- Storage/Return

Cytologic slides will be retained at the UCSF Hematopathology lab indefinitely, unless the institution requests their return.

7.3 **Mutant Allele Burden Measurement REQUIRED**

The mutant allele burden assay encompasses the DNA sequencing of all exons in each of the following genes: *NRAS*, *KRAS*, *RRAS2*, *PTPN11*, *CBL*, *NF1*, *SETBP1*, *SH2B3*, *ASXL1*, and *JAK3*. The assay is quantitative and is intended to monitor the allele burden of one or more previously uncovered mutations in a patient to assess for minimal residual disease. See [Appendix V](#) for details regarding the determination of pathogenicity.

When a patient enrolls on study, send an email to [contact] with a copy to the COG assigned Study Research Coordinator, to receive a specimen collection kit.

7.3.1 **Sample Collection and Handling Instructions**

A peripheral blood sample will be collected at the time points described below. Each sample will be utilized for the purpose of mutant allele burden measurement.

Sampling Schedule and Collection

Peripheral blood samples will be obtained at the following time points:

- A single sample collected at any time between Day -14 through Day 0, before Cycle 1 (if sent as fee-for-service, can be collected up to 30 days prior to treatment)
- Day 28 of Cycle 1
- Day 1 of every odd Cycle (3, 5, 7, etc....)
- Progressive disease (when applicable)
- End of Treatment

Sample Processing and Labeling

Collect peripheral blood samples of approximately 2-4 mL in Sodium (Na) Heparin green top tubes. Invert 5 times to ensure mixing of the anticoagulant and blood. Peripheral blood should be collected at every Mutant Allele Burden Measurement timepoint listed above.

Collect 4 buccal swabs for each cheek (8 total) by gently rolling the swab along the inside of each cheek 10 times. Place each swab inside a separate tube making sure not to touch the tips. Patient should not have any food inside the mouth at the time of collection. Buccal swabs will only be collected at the initial time point (Day -14 through Day 0, before Cycle 1).

Each tube and swab must be labeled with the patient's COG I.D., study number (ADV1521), and the date and time the sample was drawn. Data should be recorded on the Mutant Allele Burden Measurement Specimen Transmittal Form, which must accompany the sample(s).

7.3.2 **Sample Shipping Instructions**

The samples should be shipped to the UCSF Molecular Diagnostics

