10.2 Response Criteria

Response and progression will be evaluated using the tables found in [Appendix III](#). These criteria were developed by an international consensus panel. ⁴⁶

The overall response will be defined in terms of the genetic and clinical responses defined in Appendix III according to the following table:

Genetic Response	Clinical Response			
	cCR	cPR	cSD	cPD
gCR	CR	CR	CR	PD
gSD	PR	PR	SD	PD
gPD	PD	PD	PD	PD

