9) Chimerism response (only for patients after HSCT)	>15% autologous cells after allo-HSCT	Complete donor chimerism	-	50% increase and >5% increase of autologous cells and >5%	

CR: complete response, PR: partial response, PD: progressive disease, WBC: white blood cell, PB: peripheral blood, BM: bone marrow

*Myeloid precursors include promyelocytes, myelocytes, and metamyelocytes. The myeloid and erythroid precursors and blasts in PB are given as % of the total nucleated cells in PB (WBC including erythroblasts).

**in *NF-1*, *PTPN11*, *NRAS*, *KRAS*, *RRAS2*, or *CBL*, thus the mutation are thought to be initiating. In patients with germ-line *NF-1*, *PTPN11* or *CBL* mutation, only acquired mutations can be evaluated for response and relapse after therapy. The germ-line mutation remains even if patients achieved complete molecular response. The molecular response will be determined using the “JMML Mutant Allele Burden” assay.

Criteria for progression including WBC, platelet count and spleen size cannot be used in the setting of an active infection.

#Extramedullary disease includes infiltration of skin, lung, and very rarely cranial nerves or central nervous system.

Table 2: Definition of response following therapy other than HSCT in JMML

Clinical remission status: parameter 1-6 of table 1		Genetic remission status: parameter 7-9 of table 1	
Clinical complete remission (cCR)	Patient fulfills the criteria of CR of all applicable clinical variables 1-6 of table 1 The response parameters must be maintained for at least 4 weeks.	Genetic complete remission (gCR)	Defined if the patient shows a normal karyotype and absence of acquired mutations in PTPN11 , NF-1 , NRAS , KRAS , or CBL .
Clinical partial remission (cPR)	Defined if the patient does not fulfill the criteria of cCR, but vPR was achieved in at least one of clinical variables (1 – 6) and none of clinical variables showed vPD.	-	-
Clinical stable disease (cSD)	Defined if the patient does not fulfill the criteria of cCR and cPR, but none of the parameter showed vPD.	Genetic stable disease (gSD)	Defined if the patient does not fulfill the criteria of gCR, but none of the genetic parameters (7-9) showed vPD.
Clinical progressive disease (cPD)	Defined if any of the parameters 1-6 showed vPD.	Genetic progressive disease (gPD)	Defined if any of the parameters 7-9 showed vPD.

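### Section 9.8 summarises mutant allele burden only by means, SDs and 95% CIs and plans no comparison with disease activity, so it cannot address Aim 1.2.3

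*Combined protocol and SAP*

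**What the plan says.** Section 1.2 sets out Aim 1.2.3: "To prospectively evaluate mutant allele burden as a marker of disease activity in JMML". The abstract lists the same objective.

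Section 7.3 makes the assay mandatory and describes it so: "The assay is quantitative and is intended to monitor the allele burden of one or more previously uncovered mutations in a patient". Section 7.3.1 schedules peripheral blood before Cycle 1, on Day 28 of Cycle 1, on Day 1 of odd cycles, at progression and at end of treatment.

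The analysis is in Section 9.8: "Mutant allele burden (as percentages) and trametinib concentrations as measured by mass spectrometry will be analyzed descriptively". The next sentence completes it: "Values will be summarized with means, standard deviations, and 95% confidence intervals". Section 9.3 covers response rate, response duration and toxicity, and says nothing of burden.

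Burden meets disease status in one other place, the definition of response. Section 10.2 states: "The overall response will be defined in terms of the genetic and clinical responses defined in Appendix III". On the genetic side, Appendix III says that "The molecular response will be determined using the" JMML mutant allele burden assay.

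**The concern.** Whether a measurement is a marker of disease activity is a question about association: when the disease improves or worsens, does the measurement move with it? Section 9.8 describes burden alone, so even perfect execution would leave the question open.

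The question is a live one for this drug. Section 2.2.1 reports that MEK inhibition in mice improved blood counts, spleen size and survival while mutant cells persisted. Clinical improvement with little change in burden is therefore a plausible result here, and a mean of burden would not reveal it.

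At stake is a named secondary aim. If the relating analysis is chosen only after the data are seen, the aim's claim to be prospective is weakened.

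**Working it through.** **1. Figures in the plan.** No sample size, effect size or error rate is given for Aim 1.2.3. The only design figures belong to the primary endpoint. They reproduce: at a 5% response rate, the chance of stopping early is 0.95^10 = 0.599, the expected size is 10 + 10 × (1 - 0.599) = 14.01, and the type I error is 0.0686 (stated 0.069); at 25%, power is 0.882. None of this bears on the aim.

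**2. What the planned statistics can show.** A mean, SD and CI depend only on the set of burden values. Reassigning those values among patients changes none of them, but it can change the association with clinical status completely. Illustration with 20 simulated changes in burden:

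- mean -9.4, SD 8.9
- 95% CI: -9.44 ± 2.093 × 8.88/√20 = -9.44 ± 4.16, or (-13.6, -5.3)

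Ordered to agree with a clinical index, the values have a Spearman correlation of +1.0; shuffled, 0.0; reversed, -1.0. All three summaries are identical each time. The simulated values are arbitrary; the invariance is not.

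**3. Whether the response endpoint fills the gap.** In Appendix III, Table 1, the molecular variable is scored as absence (complete response) or as reappearance or new acquisition (progression). Its partial-response cell is empty. A fall from, say, 40% to 10% would therefore be genetic stable disease. The quantitative value has no use in the analysis text outside Section 9.8.

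**4. Whether the data for a comparison exist.**

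- Cycle 1 Day 28 (Section 4.2): physical examination, blood count with differential, and burden sample are all listed.
- Day 1 of odd cycles from Cycle 3 (Sections 4.4 and 7.3.1): the same three.
- End of therapy (Section 7.1): the same three, plus marrow.
- Progression (Section 7.1): the table lists the burden panel and the optional assays only, so a paired clinical measure is not assured.

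Full clinical response status at the same visit is less secure. From Cycle 3, marrow is taken only in odd cycles and only when it would settle the response classification (Section 4.4.2), and clinical complete remission must last 4 weeks (Appendix III, Table 2).

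**5. What an association estimate could deliver.** Assume one pair per patient and use the Fisher transformation, with CI = tanh(atanh(r) ± 1.96/√(n - 3)). The design has 10 evaluable patients at stage 1 and 20 in full; 24 is the enrolment maximum.

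| Assumed r | n = 10 | n = 20 | n = 24 |
|---|---|---|---|
| 0.3 | -0.41 to 0.78 | -0.16 to 0.66 | -0.12 to 0.63 |
| 0.5 | -0.19 to 0.86 | 0.07 to 0.77 | 0.12 to 0.75 |
| 0.7 | 0.13 to 0.92 | 0.37 to 0.87 | 0.41 to 0.86 |

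The correlation detectable with 80% power at two-sided 5% is tanh((1.960 + 0.842)/√(n - 3)): 0.785, 0.591 and 0.545 for n = 10, 20 and 24. Estimation is feasible. A powered test is feasible only for a strong association.

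**The case against.** The best defence is that Section 9.8 is brief rather than wrong. It promises a descriptive analysis, and nothing in it excludes summaries by clinical response or of change from baseline. That is true, and a reader should not infer that the plan rules out such a comparison. It plans none, however, and the statistics it does name cannot supply one.

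A second defence is scale. This is one of five secondary aims in a small single-arm trial, no decision rule uses it, and the intervals above are wide. That stands as a reason to ask for estimation rather than a test. It does not justify leaving the relation out.

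Two stronger readings are tempting, and the documents do not support either.

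- *Germline alleles will be averaged into the burden.* Section 9.8 does not say so. For patients with germline mutations, the Appendix III note says that "only acquired mutations can be evaluated for response and relapse after therapy"; Section 7.3.1 collects buccal swabs at baseline; Appendix V compares tumour and normal samples. At most, Section 9.8 omits to repeat the rule.
- *Later means will cover only patients still on treatment, so a falling mean may be an artefact of dropout.* Sections 7.1 and 7.3.1 require samples at progression and at end of treatment, and Section 9.8 does not exclude them. The bias would arise only if means were taken by scheduled visit without those samples, and the documents give no figures from which to size it.

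**Conclusion.** The point holds as a mismatch between aim and method: the stated summaries carry no information on whether burden follows the disease, and no other section provides the comparison. It rests on reading Section 9.8 together with 9.3, 10.2 and Appendix III, not on any assumed figure; the simulated values and correlations only illustrate.

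Its reach is limited to Aim 1.2.3. Neither the response rate nor the stopping rule changes. It should be corrected, because a stated aim otherwise has no analysis that addresses it and the remedy is cheap. The remedy will not make the answer precise: with 20 patients and a true correlation of 0.5, the interval would run from about 0.07 to 0.77.

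**What to change.** Add a paragraph to Section 9.8 that states:

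- **Main estimate.** Within-patient change from baseline in acquired-mutation burden, related to clinical measures at the same visit: WBC, platelets, peripheral precursors and blasts, and palpated spleen size. A rank correlation, or a repeated-measures estimate that allows for several visits per patient, with a 95% CI and no powered test.
- **Supporting summary.** Change in burden by best clinical response on variables 1-6 of Appendix III, where assessable.
- **Comparator.** Not overall response: the same assay helps to define it, and Section 10.2 already counts genetic complete remission with clinically stable disease as CR, so the comparison would be partly circular.
- **Samples.** Progression and end-of-treatment samples are included, paired with clinical measures where these were taken.
- **Variants.** Only acquired variants are used, in line with the Appendix III note, with a rule for patients who have several mutations, germline mutations only, or none detectable.

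The burden schedule should also be reconciled, since it decides which values pair: Section 7.3.1 gives Day 1 of odd cycles, the delivery map for Cycle 3 onward lists the sample on Day 1 of each cycle, and Section 4.4.3 refers to collection at the end of odd cycles.

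The cost is a paragraph, a little extra analysis and wide intervals at this sample size. No new samples or visits are needed for the main estimate, though some progression samples may lack a paired clinical measure.
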